The STROKESTOP II study investigates the potential of NT-proBNP as a stratification tool to improve efficacy of AF screening in a randomized population-based study.³⁵ High and low risk groups were defined according to a cutoff of NT-proBNP $\geq 125\text{ng/L}$. New AF was detected in 2.6% of all patients and 4.4% in the high risk group. A recent subgroup analysis from the randomized LOOP study³⁶ suggests that in an older population with additional stroke risk factors, ILR screening is associated with a significant reduction in stroke risk among participants with baseline NT-proBNP above median but not among those having lower levels.³⁶ These results support the potential of NT-proBNP to improve the benefit of AF screening and possibly aid in risk stratification for preventive treatment. However, the utility of NT-proBNP for targeting AF screening and prevention of AF consequences needs to be addressed in well-designed randomized trials.

The risk of IS in patients with AF is presumed to arise from emboli generated by structural and functional alterations within the atria, where a pro-thrombotic milieu is established, particularly in the left atrial appendage.³⁷ Consequently, a new concept of atrial cardiomyopathy has evolved, defined by complex structural, functional and electrophysiological changes, affecting the atria with the potential to produce clinically relevant manifestations.³⁸ Several transthoracic echocardiographic parameters have emerged as promising biomarkers of AF. These include left arterial volume and left arterial function assessed by strain which are associated with AF in patients at risk^{39,40} and in patients with IS of undetermined source.^{41,42} However, knowledge of association between echocardiographic parameters and paroxysmal AF in a general population is limited.

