The study design enables cross-sectional and longitudinal assessments of associations between AF and repeated measured traditional risk factors, echocardiographic measures, findings on MRI of the brain, and results of cognitive tests. Long term follow-up enables comparison of the group undergoing ECG247 monitoring to those who have not undergone ECG247 monitoring regarding clinical outcomes (after 6 years).

Study population: A total of 4000 individuals from the general population with NT-proBNP > median fulfilling the inclusion criteria will be included after informed consent for study participation.

Inclusion criteria:

- Age ≥40 years
- NT-proBNP > median level
- Informed consent for participation

Exclusion criteria:

- History of AF (self-reported)
- Use of anticoagulation therapy
- Pacemaker/CRT device
- No available smart phone

Study procedure: Individuals with NT-proBNP > median will be identified when attending the second visit of the Tromsø Study. Eligible participants will be included and automatically randomized (1:1) to ECG247 monitoring or no ECG monitoring. Participants not responding will receive two reminders. Invitation will continue until 4000 study participants have been included.

Intervention: The AF screening device will be sent by post from the study centre to all participants in the intervention group at inclusion, free-of-charge. User guides (paper, digital and video) will be prepared (Norwegian and English), and an "help-desk" located at the Tromsø Study will be available for phone/video assistance. The monitoring of included participants will be handled by trained research nurses. All participants will be requested to fill in a digital questionnaire after having completed the test focusing on usability and adverse events. All ECG recordings will be reviewed by a group of trained and experienced study nurses and physicians. Cardiologists will supervise and verify pathologic ECG findings. The following variables will be registered: Heart rhythm (sinus rhythm, AF, atrial flutter, supraventricular tachycardias (SVT),

[figure not shown]

Figure 1: Illustration of ECG247 technical setup, modified from www.ecg247.com

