Power estimates: Power estimates are customized to test the primary hypothesis that continuous ECG-monitoring in individuals with elevated NT-proBNP and subsequent anticoagulant treatment according to current international guidelines leads to reduced incidence of the composite outcome IS and cardiovascular death. According to a previous study performed at Sørlandet⁵⁰ with ECG247 the number needed to screen was 45 to detect one unrecognized case of AF in subjects at risk for stroke. When restricting screening to the population with NT-proBNP level > median the number needed to screen may be reduced to 31³⁶ and even 23³⁵ in an older population. The 6-year risk of the composite outcome is expected to be 4% in the control group. Risk in the group screened where no AF is found varies from 2 to 3%. In the group screened where AF is found the risk is 10% (30% risk of IS during a 6-year period, reduced by 70% with oral anticoagulant therapy). If the 6-year risk among screened participants without AF is 2.2%, and we include 2000 participants in each group, there is 80% power to detect a significant difference ($\alpha=0.05$) between control and intervention groups with estimated risk of 4.0% vs. 2.4% for the composite outcome, respectively. Based on the results of the Loop and StrokeStop study and the younger population in the Tromsø study, we expect to reduce risk of the composite outcome from 4% in the control group to 2.4% in the screening group. Compared to previous epidemiological studies, the planned epidemiological projects for the PhD student will have sufficient statistical power to explore meaningful associations.

Data handling and storage: EUTRO is a research administrative tool that will be used for data collection and storage in Tromsø 8. EUTRO provides a complete overview of a study's total research material, including responses to questionnaires, biological material, health data, and project information. EUTRO is integrated within TSD (services for sensitive data located at University of Oslo) which assures and facilitates anonymized data handling and storage according to present regulations and research needs. All data security is taken care of according to the requirements from the Norwegian Data Protection Authority, and privacy is well maintained in the system. The system ensures compliance with the Health Research Act and GDPR requirements for security, handling, and administration of sensitive research data and biological material.

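### Does the entry criterion of NT-proBNP above the median, given without a value or a reference population, undermine the trial's population or its sample size?

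*Protocol*

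**What the plan says.** The inclusion criteria in section 1.3 of the Protocol list "NT-proBNP > median level", with no value and no reference population. Under Study procedure, "Individuals with NT-proBNP > median will be identified when attending the second visit of the Tromsø Study", and then "Eligible participants will be included and automatically randomized (1:1) to ECG247 monitoring or no ECG monitoring". Recruitment is open-ended up to the target: "Invitation will continue until 4000 study participants have been included".

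The Power estimates paragraph starts from a number needed to screen of 45 in people at risk of stroke. It continues "When restricting screening to the population with NT-proBNP level > median the number needed to screen may be reduced to" 31, from one cited study, and even 23, from another, with the remark that this is in an older population. The sizing follows: "If the 6-year risk among screened participants without AF is 2.2%, and we include 2000 participants in each group", power is 80% for 4.0% against 2.4%. The risk when AF is found is given as 10%, explained as 30% reduced by 70%.

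Section 1.1 describes the study behind the 23: "High and low risk groups were defined according to a cutoff of NT-proBNP" of 125 ng/L or more, and "New AF was detected in 2.6% of all patients and 4.4% in the high risk group".

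**The concern.** Three things look wrong.

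- **An undefined cut-off.** If the median is that of visit 2 attendees, it is unknown while they are still attending and being randomised. If it comes from elsewhere, the share of attendees above it is unknown. A running median would make the same NT-proBNP value eligible at one time and not at another.
- **One label for different thresholds.** The power paragraph calls both 31 and 23 results above the median. Section 1.1 shows that 23 belongs to a fixed threshold, and that the median behind 31 is that of an older cohort with added stroke risk factors.
- **A sized risk that seems to match neither figure.** With 10% and 2.2% as components, 2.4% corresponds to a number needed to screen of 39.

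At stake would be the population to which the result applies, the claimed power, and whether 4000 people can be found. If half of 10 000 visit 2 invitees lie above the cut-off, 4000/(10 000 × 0.5) = 80% of them must attend, be eligible and consent.

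**Working it through.** **Inputs** (section 1.3, Power estimates, unless noted): control risk 4.0%; risk without AF 2.2%; risk with AF found 10%, or 30% × (1 − 0.70) = 9% from the explanation given beside it; numbers needed to screen (NNS) 45, 31 and 23; 2000 per group; α = 0.05, taken as two-sided because the Protocol does not say. From section 1.1: 4.4% new AF at 125 ng/L or more.

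**Step 1: the stated power.** Two proportions, no continuity correction. The mean risk is 3.2%.
- Null SE = √(2 × 0.032 × 0.968/2000) = 0.005566
- Alternative SE = √(0.04 × 0.96/2000 + 0.024 × 0.976/2000) = 0.005560
- Power = Φ((0.016 − 1.96 × 0.005566)/0.005560) = 82.0%

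For 80% power the requirement is 1899 per group, or 2022 with continuity correction. The claim of 80% with 2000 reproduces.

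**Step 2: the origin of 23.** 1/0.044 = 22.7, so it is the result at 125 ng/L or more. The label in the power paragraph is loose.

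**Step 3: which yield gives 2.4%.** Screening-arm risk = 2.2% × (1 − 1/NNS) + r × 1/NNS, where r is the risk with AF found. Power is against 4.0%.

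| NNS | Risk, r = 10% | Power | Risk, r = 9% | Power |
|---|---|---|---|---|
| 45 | 2.37% | 83.4% | 2.35% | 84.5% |
| 31 | 2.45% | 79.2% | 2.42% | 81.0% |
| 23 | 2.54% | 73.8% | 2.50% | 76.6% |

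Solving for exactly 2.4% gives a yield of 0.2/7.8 = 2.56% (NNS 39) at r = 10%, or 0.2/6.8 = 2.94% (NNS 34) at r = 9%. Both lie between the 45 and the 31 that the Protocol quotes. At r = 9%, 31 rounds to the stated 2.4%. At r = 10% it misses by 0.05 percentage points and leaves power within one point of 80%.

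**Step 4: can the table be read as the cost of a vague cut-off?** No. In it, power falls as screening finds more AF. That happens only because control risk is held at 4.0% and no-AF risk at 2.2% while the yield varies. Suppose instead that undetected AF in controls carries the 30% risk that the Protocol assigns to untreated AF. Control risk is then 2.2% × (1 − 1/NNS) + 30% × 1/NNS. With r = 10% in the screened arm:

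| NNS | Control | Screened | Difference | Power |
|---|---|---|---|---|
| 45 | 2.82% | 2.37% | 0.44 points | 14% |
| 23 | 3.41% | 2.54% | 0.87 points | 37% |

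The direction reverses: more AF found means more power. Recomputing power from the yield at a named cut-off, with the other inputs fixed, would therefore mislead. The low levels here, and the 22% to 30% power when the no-AF risk is 3.0% (the top of the Protocol's own range), concern the 4.0% and 2.2% inputs. That is a separate question from how the cut-off is defined.

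**The case for a change.** The strongest case for a change is that eligibility belongs in a protocol and is not normally left to an analysis plan. A criterion with neither a number nor a reference population cannot be applied as written, and the two cited yields come from thresholds that are not shown to be this trial's. Naming a value would cost a sentence.

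The factual part stands: the value and its source are not given, and 23 is mislabelled. It goes no further, for these reasons:

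- Nobody can be selected and randomised until a number exists, so the gap closes in operation. Section 3.2 says that selection follows the NT-proBNP results. No text describes a running median, and a cut-off fixed in advance is compatible with everything written.
- Both arms are drawn from the same side of whatever cut-off is used, so its definition cannot bias the comparison. The value and its source can be reported with the baseline data.
- The Protocol itself marks 23 as an older-population figure and says only that the number needed to screen may be reduced. It also calls the Tromsø population younger, so a sized yield below those of the older cohorts is coherent.
- The 80% joint yield is a real recruitment demand, but it rests on an assumed share above the cut-off. Stating a value in ng/L would not by itself ease it. The Protocol's answer is to go on recruiting until the target is met.

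**Conclusion.** No change follows. The missing value is a detail that the team has to supply before the first randomisation, and the label on 23 is a slip in a background figure from which the 2.4% does not follow. The stated sizing reproduces: 82% power uncorrected, and 2022 per group with continuity correction against the planned 2000. A number needed to screen of 31 gives 79% to 81%, depending on whether the risk with AF found is 10% or 9%.

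This rests on a two-sided 5% test, on the Protocol's own inputs of 4.0% and 2.2% (used here without endorsing them), and on the cut-off being fixed before randomisation. If it were instead recalculated during recruitment, the arms would still be comparable, but the enrolled population would be harder to describe. A reader may reasonably want the cut-off and its source population stated, and 23 tied to 125 ng/L or more. Doing so would alter no analysis, target or conclusion.

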2. IMPACT

2.1. POTENTIAL IMPACT OF THE PROPOSED RESEARCH

The study will provide new knowledge about risk factors, clinical findings and co-existing comorbidities in individuals that are associated with both increased risk of AF and clinical events. Hence, the study can contribute to identifying new targets and better tools for a more effective, precise and personalized prevention of stroke in patients with AF and provide knowledge about risk groups where long-term ECG monitoring would be beneficial. The project will provide novel insights into the impact of screening on HRQoL in participants who have AF confirmed through screening. In addition, the study will provide data on the prevalence of paroxysmal AF and AF burden detected by new sensor technology both being highly relevant outcomes and risk factors for future Tromsø-Study projects.

In the long term, we will generate new knowledge on whether AF screening utilizing patients centered novel sensor technology in participants with elevated level of NT-proBNP is beneficial for patients' outcomes. The study may impact future European guidelines for the prevention and treatment of AF.

The proposal adds clinical experience and skills related in the use of sensor technology for home-based monitoring of cardiac patients and patient-administered heart rhythm examinations without the need for hospital visits. Hence, more patients may gain benefit from this cost-effective and sustainable non-invasive approach for AF detection. Reducing the need for healthcare resources, transportation, hospital stays away from home and work has the potential of moving health care towards more precise diagnostics and equal care in a sustainable manner, and also be beneficial for health-related costs and the environment.

Using new sensor technology, some participants will through the trial be diagnosed with AF, that they were previously unaware of. This enables initiation of effective preventive treatment that reduces the risk of stroke. Successful self-screening makes AF screening possible at a population level, and consequently has a potential to prevent mortality and severe AF-related morbidity.

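### The only usability and adverse-event questionnaire is tied to completing the test, so non-starters are not asked, early stoppers may not be, and tolerability statements will probably be too favourable

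*Protocol*

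**What the plan says.** All of the collection rules are in protocol section 1.3.

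- **Allocation and delivery.** "Eligible participants will be included and automatically randomized (1:1) to ECG247 monitoring or no ECG monitoring". The sensor then goes out by mail: "The AF screening device will be sent by post from the study centre to all participants in the intervention group at inclusion, free-of-charge". Participants apply it themselves and connect it to a smartphone by Bluetooth.
- **Usability and adverse events.** "All participants will be requested to fill in a digital questionnaire after having completed the test focusing on usability and adverse events". No other instrument for either is described.
- **Support.** A help-desk "located at the Tromsø Study will be available for phone/video assistance". Research nurses handle the monitoring.
- **What is registered from the recording.** Rhythm, timing, duration and rate of arrhythmias, symptoms, and how long the recording lasted. Reasons for not starting or for stopping are not listed.
- **Later contact.** The assessment six months after the intervention covers HRQoL and medication.
- **Safety paragraph.** It deals with arrhythmias and other abnormal cardiac findings, not with problems caused by the device.

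Section 2.1 shows how experience with the sensor is meant to be used: "Successful self-screening makes AF screening possible at a population level".

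**The concern.** A questionnaire triggered by finishing the test selects people partly on what it measures. Someone who cannot pair the sensor or never manages to put it on has not completed anything and, on any ordinary reading, gets no questionnaire. Someone who takes it off early, for example because of a skin reaction, may or may not get one. Both groups are where one would look for usability problems, and the second is also where device-related adverse events would be expected.

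At stake are the ancillary statements on how well self-screening works and is tolerated. Section 1.2 asks whether this tool can simplify AF screening, and section 2.1 links population screening to self-screening that succeeds. Both concern everyone who is sent a sensor, not only those for whom it went smoothly.

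This cannot be left to an analysis plan, which cannot recover answers that were never requested. Who is asked, and when, has to be settled before sensors are posted.

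**Working it through.** **Step 1. Who is reached by each stated route** (protocol section 1.3).

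| Route | Completers | Early stoppers | Never started |
|---|---|---|---|
| Post-test questionnaire | yes | unclear, completion undefined | no |
| Recording duration | yes | yes, but no reason | absence of a recording visible, no reason |
| Help-desk | if they call; no recording of problems described | same | same |
| Safety paragraph | detected arrhythmias and abnormal findings only | same | not applicable |
| Six-month contact | HRQoL and medication only | same | same |

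The opening words about all participants do not close the gap. The control half has no ECG monitoring and so no test to complete, which means the phrase cannot be literal. No other route asks about usability, device-related events or reasons for stopping.

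**Step 2. How many people are concerned.** The power paragraph plans 2000 per group. The protocol states no completion rate, so assume a completion share c of 95% to 70%. The number not completing is 2000 × (1 − c), which is 100 at 95%, 200 at 90%, 400 at 80% and 600 at 70%.

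**Step 3. Illustration for usability problems.** The plan gives no figure to reproduce. Let a be the problem rate in completers and b the rate in all others. The rate over everyone sent a sensor is

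c × a + (1 − c) × b,

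while a completers-only questionnaire shows a. Assume a = 5% and b = 20%, and take the strict case in which no early stopper is asked.

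| c | Rate over all sent | Rate in completers | Understatement of the rate, 1 − a/rate | Share of affected people not asked, (1 − c)b/rate |
|---|---|---|---|---|
| 90% | 4.5 + 2.0 = 6.5% | 5% | 23% | 2.0/6.5 = 31% |
| 80% | 4.0 + 4.0 = 8.0% | 5% | 38% | 4.0/8.0 = 50% |
| 70% | 3.5 + 6.0 = 9.5% | 5% | 47% | 6.0/9.5 = 63% |

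The last two columns are different quantities and should not be interchanged. The result depends heavily on b. With b = 40% and c = 80% the rate over all sent is 12.0%; with b = 5% there is no bias at any c.

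**Step 4. Adverse events need a different denominator.** A person who never applies the patch cannot have a skin reaction to it. Assume 80% complete (rate 5%), 5% stop early (rate 20%) and 15% never start (rate 0).

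- Over all sent: 0.80 × 5% + 0.05 × 20% + 0.15 × 0 = 5.0%, the same as in completers.
- Over all who applied the sensor: (4.0% + 1.0%)/0.85 = 5.9%.

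For device-related events, the group of interest is therefore everyone who applied the sensor, early stoppers included. Dividing by all sent can hide the excess.

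**The case against.** The strongest reply is that the sentence fixes when people are asked, not who is excluded. The documents reviewed give no monitoring period, minimum wear time or definition of completion, so a person who removes the sensor early may simply have ended the test and be asked. That stands for early stoppers, and a reader who infers that all of them are left out goes further than the text. It does not help those who never started.

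Second, the protocol states no rate, analysis or denominator for this questionnaire. A reader might infer that adverse events will be reported over completers only, but the documents do not say so. What they do fix is who is asked, and that limits what can later be reported.

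Third, much is already countable. The centre knows how many sensors it posts, and recording duration is registered, so non-start and short recordings can be counted across everyone sent a device. That also stands. What is missing is the reason, and the experience of the people concerned.

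Fourth, the direction of the bias is not assured. Step 4 shows that never-starters can offset early stoppers in an adverse-event rate, and non-response among completers can move the figure either way. For usability, the expected direction is clearer, because a problem with the device is itself a plausible cause of not starting or not finishing.

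Fifth, usability and adverse events are in neither the primary composite nor the four research questions. This is correct and limits the reach of the point.

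**Conclusion.** The point holds as a weakness in ancillary data collection. As written, participants who never start are not asked about usability or adverse events, early stoppers may not be, and reasons for non-use or stopping are recorded nowhere in the text available. A part of the protocol between sections 2.2 and 3.2 was not available to check.

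Statements about usability and tolerability of self-screening would probably be too favourable. This rests on the assumption that problems are commoner in people who do not finish; if they are equally common, there is no bias. The size cannot be computed from the documents. The figures of 6.5% to 9.5% against 5% illustrate assumed rates and do not estimate what this trial will find.

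A reader might take this as a threat to the trial's main conclusion. The documents do not support that: the composite outcome comes from registry linkage, the comparison is between randomised groups, and neither depends on this questionnaire. The design figures of "estimated risk of 4.0% vs. 2.4% for the composite outcome, respectively" are untouched.

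**What to change.** In the Intervention paragraph of section 1.3:

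1. Send the questionnaire to every participant allocated to ECG247 at a fixed interval after the sensor is posted, whether or not the test was started or finished.
2. Add one item on whether recording was not started or was stopped early, and why.
3. State the denominators. Report usability and non-start or early stop over all participants sent a device, and device-related adverse events over all who applied the sensor, early stoppers included. Give completers as a secondary figure for both.

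The cost is a changed trigger date, one extra item and a few hundred more digital requests at most (100 to 600 over the assumed completion range). Response will probably be lower among people who did not complete, so some selection will remain. The number asked and the number answering in each group should be reported so that readers can judge it.
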